4.10 Therapy Delivery Map – Subsequent Cycles of Therapy		
This therapy delivery map applies to all cycles given after Cycle 1: Pazopanib treatment given once daily continuously for 28 days (1 cycle = 28 days). Patient may receive additional cycles (if they meet requirements		
described in Section 4.2.	Patient name/initials	DOB

See Section 4.2 for criteria for starting next cycle.

DRUG	ROUTE	DOSAGE Circle applicable formulation and strikethrough unused formulation to avoid confusion	DAYS	IMPORTANT NOTES	OBSERVATIONS OBTAIN OTHER ASSESSMENTS AS REQUIRED FOR GOOD PATIENT CARE
Pazopanib (GW786034) IND# 065747	РО	If tablets: 450 mg/m ² /dose given once daily (Max dose: 800 mg) If powder in suspension: 225mg/m ² /dose given once daily (Max dose: 400 mg)	1-28	Take on an empty stomach (at least 1 hour before a meal or 2 hours after a meal). See Section 4.1 for further details.	 a History, physical exam, vital signs, blood pressure b Urinalysis (including UPC) and/or 24 hour urine for protein c Ht, Wt, BSA, performance status d CBC, differential, platelets, electrolytes including K⁺, Ca⁺⁺, PO4³, Mg ⁺/_c reatinine, total protein, albumin, ALT, bilirubin, amylase, lipase e Pregnancy test f TSH g PT/PTT/INR h ECHO, EKG, plain x-ray of knee (see Section 7.2.1) i Disease evaluation including BMA/Bx, Urine VMA/HVA, AFP as indicated (see Section 7.1). j PK (see Section 7.3 & Appendix VI). k PD (see Sections 7.1 and 7.4)

Cycle of Therapy:_____ Ht____cm Wt___kg BSA___m²

Date	Date	Week	Day	Pazopanib	Assessments	Comments (Include any held
Due	Given			mg		doses, or dose modifications)
				Enter calculated dose above and t	hen dose administered below	
		1	1	mg	$a^{1}, b^{2}, c^{2}, d^{3}, e^{2}, f^{4}, g^{5}, h^{6}, i^{4}, j^{7}, k^{8}$	
			2	mg		
			3	mg		
			4	mg		
			5	mg		
			6	mg		
			7	mg		
		2	8	mg	d ³	
			9	mg		
			10	mg		
			11	mg		
			12	mg		
			13	mg		
			14	mg		
		3	15	mg	a^{1}, d^{3}	
			16	mg		
			17	mg		
			18	mg		
			19	mg		
			20	mg		
			21	mg		
		4	22	mg	d ³	
			23	mg		
			24	mg		
			25	mg		
			26	mg		

	27	mg		
	28	mg		
		See Section 4.2 for criteria for starting r modifications.	ext cycle. See section 5 for dose	

 $^1\,\mathrm{Every}$ other week for Cycle 2 and 3, and then prior to the start of each subsequent cycle.

² Prior to the start of each subsequent cycle.

³ Weekly during Cycle 2, every other week in Cycle 3, and then prior to the start of each subsequent cycle.

⁴ Prior to Cycle 3, 5, 8, and 11 and every 3rd cycle thereafter
⁵ Prior to Cycle 3 and every 6 cycles thereafter
⁶ Prior to Cycle 2 and Cycle 5, and then every 6 cycles.
⁷ Pre-dose at every odd cycle.
⁸ Pre-dose on either Day 1 of Cycle 2 or Day 1 of Cycle 3.

5 DEFINITIONS AND DOSE MODIFICATION FOR TOXICITY

All dose modifications should be based on the worst preceding toxicity. The severity of adverse events will be graded utilizing the National Cancer Institute (NCI) CTCAE, version 4.

The cycle duration remains 28 consecutive days in patients who have dose interruption.

5.1 Definition of Dose Limiting Toxicity (DLT)

DLT will be defined as any of the following events that are at least possibly, probably, or definitely attributable to pazopanib. See Section 5.4 for the Potential Pazopanib Specific Side Effects. Dose-limiting hematological and non-hematological toxicities are defined differently.

5.1.1 Hematological Dose-Limiting Toxicity

- a) For patients who are evaluable for hematologic toxicity assessment (patients **without** bone marrow involvement)
 - Grade 4 Thrombocytopenia (platelet count < 25,000/mm3) or Grade 4 neutropenia
 - Any hematologic toxicity requiring dose reduction or treatment interruption for >14 days

b) For all patients:

- \geq Grade 2 arterial thromboembolic events (visceral arterial ischemia, peripheral ischemia, or ischemia cerebrovascular)
- Grade 3 or 4 venous thromboembolic event
- Any thrombotic event (other than central venous line [CVL] associated thrombosis) requiring systemic anticoagulation

5.1.2 Non-Hematological Dose-Limiting Toxicity

- 5.1.2.1 Any Grade 4 non-hematologic toxicity
- 5.1.2.2 Any Grade 3 non-hematological toxicity, with the specific exclusion of the following:
 - Grade 3 nausea and vomiting of less < 3 days duration
 - Grade 3 fever or infection,
 - Grade 3 hypophosphatemia, hypokalemia, hypocalcemia or hypomagnesemia responsive to oral supplementation within 7 days of start of supplement (see Section 5.4.4 for dose modifications)
- 5.1.2.3 Grade 2 allergic reactions that necessitate discontinuation of protocol therapy will not be considered a dose-limiting toxicity.
- 5.1.2.4 Any Grade 2 non-hematological toxicity that persists for \geq 7 days and is considered sufficiently medically significant or sufficiently intolerable by patients that it requires treatment interruption may also be considered a DLT following discussion with the Study chair and a Novartis Medical Lead.
- 5.1.2.5 Hypertension will be graded according to the NCI CTCAE; however, dose limiting hypertension will be considered as the following:

- Grade 4 hypertension
- A blood pressure >25 mmHg above the 95th percentile for age, height, and gender (see Appendix V) confirmed by repeated measurement on the same day (See Sections 5.4.1 and 4.1.5.1 for management)
- In patients already on anti-hypertensive therapy due to previous hypertension (see Section 3.2.8.5), any blood pressure 1-25 mmHg above the 95th percentile for age, height, and gender (Appendix V) for > 14 days (See Sections 5.4.1 and 4.1.5.1 for management)

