Drug dosing for the tablet formulation should be determined using the dosing nomogram in Appendix II. For patients receiving powder for suspension (50 mg/mL), the dose will be rounded to the nearest 5 mg. Drug doses should be adjusted based on the BSA as determined by the height and weight obtained within 1 week prior to the beginning of each cycle.

Pazopanib should be taken on an empty stomach (at least 1 hour before a meal or 2 hours after a meal) at approximately the same time each day. Pazopanib tablets should be taken with clear liquids (approximately 4 ounces for children < 12 years of age and 4-8 ounces for children ≥ 12 years of age). Pazopanib suspension should be taken according to instructions in Appendix VII.

The pazopanib suspension should be swirled for at least 30 seconds prior to removal of the dose from the bottle, which should be given immediately. If a patient vomits after a dose of pazopanib, the dose should not be repeated.

A patient diary (see Appendices IA and IB) should be completed by the patient or their guardian and collected at the end of each cycle.

See Section 5 for Dose Modifications in Response to Toxicities

4.1.1 Dose Reduction

For patients who receive pazopanib tablets: Dose reduction(s) in response to toxicity may be implemented according to guidance in Sections 5.2, 5.3, and 5.4 of the protocol. Outside the specific management guidance described in these sections, patients who recover from an adverse event to starting criteria as outlined in Section 4.2 within 14 days following planned administration will also be permitted to receive protocol therapy at a reduced dose. Dose reduction(s) will be based on the starting dose and should follow the Dosing Nomogram in Appendix II.

Note: For patients receiving pazopanib tablets at a starting dose of 400 mg, there will only be one allowed dose reduction due to tablet size.

For patients who receive pazopanib as oral powder for suspension:

Dose reduction(s) in response to toxicity may be implemented according to guidance in Sections 5.2, 5.3 and 5.4 of the protocol. Outside the specific management guidance described in these sections, patients who recover from an adverse event to starting criteria as outlined in Section 4.2 within 14 days following planned administration will also be permitted to receive protocol therapy at a reduced dose. Dose reduction(s) will be based on the starting dose and should follow the guidance in Table 1 and Table 1a.

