4.2 Criteria for Starting Subsequent Cycles

A cycle may be repeated every 28 days if the patient has at least stable disease or progressive disease is ruled out based on clinical or laboratory evidence and met the clinical and laboratory parameters as defined by the guidelines for dose modification and toxicity management (Section 5) and does not have a dose limiting toxicity requiring permanent removal from protocol therapy (Section 5.1). A patient may resume protocol therapy at the same or a reduced dose if they have a toxicity that is adequately managed (eg: myelosuppression, hypertension, hepatotoxicity, electrolyte abnormality, bleeding, wound healing, etc) as outlined in Sections 5.2, 5.3, and 5.4.

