5.2 Dose Modifications for Hematologic Toxicity

All dose modifications should be based on the worst preceding toxicity.

Pazopanib tablets: For step-wise dose reductions, see Appendix II for the dosing nomogram.

Pazopanib powder in suspension: For step-wise dose reductions see Tables 1 and 1a (Section 4.1.1).

5.2.1 For all patients:

If Grade 4 neutropenia occurs,

- a) Pazopanib should be held.
- b) CBCs should be checked at least twice a week (every 3 to 4 days) until ANC $\geq 750/\mu L$.
- c) Subsequent doses of pazopanib should be given at a reduced dose, when $ANC \ge 750/\mu L$.

If Grade 4 thrombocytopenia occurs,

- a) Pazopanib should be held.
- b) CBCs should be checked at least twice a week (every 3 to 4 days) until platelet count \geq 75,000/µL without need for platelet transfusion in the preceding 7 days.

Subsequent doses of pazopanib should be given at a reduced dose, when platelet count \geq 75,000/µL without need for platelet transfusion in the preceding 7 days.

- 5.2.1.1 If dose-limiting myelosuppression occurs as noted in Section 5.1.1,
 - a) The dose of pazopanib should be resumed at a reduced dose, once ANC $\geq 750/\mu L$ and platelet count $\geq 75,000/\mu L$ without need for platelet transfusion in the preceding 7 days.
- 5.2.2 For patients who have a dose limiting hematological toxicity that does not resolve to the parameters defined in Section 5.2.1 within 14 days of holding pazopanib: if re-challenge is to be considered the Study Chair must be contacted and provide approval prior to re-challenge.

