5.4.8 Bleeding	
----------------	--

	Dose Modifications & Evaluations
Grade 1	Continue pazopanib at the current dose
	and monitor as clinically indicated.
Grade 2	1. Hold pazopanib until bleeding
	resolves to \leq Grade 1
	2. Restart pazopanib at a reduced
	dose; monitor as clinically
	indicated
Grade 3 or higher	Discontinue pazopanib permanently
OR	and remove from protocol therapy
Recurrent \geq Grade 2 event after dose	
interruption/reduction	

5.4.9 VascularThrombosis:

	Dose Modifications & Evaluations
Grade 2	Continue pazopanib at the current dose and monitor as clinically indicated.

Grade 3 (CVL associated only)	 Hold pazopanib Treat thrombosis according to institutional standards; would consider removal of the CVL. Resume pazopanib when all symptoms have resolved. If anticoagulation is required, use with caution.
All non-CVL associated Grade 3 AND all Grade 4	Discontinue pazopanib permanently and remove from protocol therapy

6

DRUG INFORMATION

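### A Grade 2 arterial thromboembolic event is a DLT under Protocol 5.1.1(b), yet the only Grade 2 row of 5.4.9 says to continue at full dose, and no section expressly orders a hold for peripheral or cerebrovascular ischemia at that grade

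*Protocol*

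**What the plan says.** Protocol 5.1 counts a listed event as a DLT when it is at least possibly attributable to pazopanib. The first criterion in 5.1.1(b), which applies to all patients and to the stated grade or higher, is "Grade 2 arterial thromboembolic events (visceral arterial ischemia, peripheral ischemia, or ischemia cerebrovascular". Venous events in the same list count by grade only from Grade 3. Section 5.1 also sends the reader onward: "See Section 5.4 for the Potential Pazopanib Specific Side Effects".

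The matching table is 5.4.9, Vascular Thrombosis. It has three rows:

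- Grade 2: "Continue pazopanib at the current dose and monitor as clinically indicated".
- Grade 3 associated with a central venous line: hold, treat, and resume once symptoms have gone.
- "All non-CVL associated Grade 3 AND all Grade 4": stop permanently and remove from protocol therapy.

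Neither the title nor any row separates arterial from venous events.

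**The concern.** The arterial threshold in 5.1.1(b) is set lower than the graded venous one, so the protocol treats a Grade 2 arterial event as the more serious. The table a site would consult for its dosing does not carry that distinction. A site that follows 5.4.9 could keep a child with drug-related Grade 2 cerebrovascular ischemia on full dose and still be compliant, although the protocol itself calls the event dose-limiting.

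Two other parts of the protocol show that the risk was in view. Section 2.3.2 lists cerebral ischemia among the uncommon but serious events seen with pazopanib in adults. Section 3.3.5.2 excludes patients who had an arterial event, including TIA or CVA, in the six months before enrollment.

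**Working it through.** There is no plan figure to reproduce. The check is whether any section requires a hold for an attributable Grade 2 arterial event.

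| Protocol section | Scope | Effect on a Grade 2 arterial DLT |
|---|---|---|
| 5.2.1, 5.2.1.1 | Neutropenia, thrombocytopenia, myelosuppression | Does not apply |
| 5.2.2 | Re-challenge after a "dose limiting hematological toxicity that does not resolve to the parameters defined in Section 5.2.1 within 14 days of holding pazopanib" | Assumes a hold but orders none; the recovery parameters are ANC and platelets |
| 5.3.1 | Non-hematologic DLTs of 5.1.2 | Orders a hold, but the arterial criterion sits in 5.1.1; item (b) sends pazopanib-specific toxicities back to 5.4 |
| 5.1.2.4 | Persistent Grade 2 non-hematologic toxicity that needs interruption | Discretionary, after discussion with the Study Chair and the sponsor's medical lead |
| 4.1.1 | Recovery within 14 days, outside the specific guidance | Patients "will also be permitted to receive protocol therapy at a reduced dose"; a permission, not a hold |
| 4.2 | Starting further cycles | "A patient may resume protocol therapy at the same or a reduced dose if they have a toxicity that is adequately managed"; a permission that includes the same dose |
| 4.5.1 | Anticoagulant use on study | Leaves continuation to the investigator |
| 5.4.2 | Severe abdominal pain or a worrying abdominal examination | Orders a hold on symptoms; reaches some visceral ischemia only |
| 8.1(b), 8.1(f) | Removal from therapy | (b) refers back to Section 5; (f) is physician judgement |

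The SAP adds no dose rule. Its section 11.2 only lists and counts DLTs.

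There are two ways to read 5.4.9.

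1. It covers arterial events. Then Grade 2 is told to continue. An arterial event at Grade 3 or 4 falls in the last row and stops permanently, so the conflict is confined to Grade 2.
2. It covers venous events only. Then nothing tells the site to continue, but arterial DLTs have no dose rule of their own at any grade.

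The neighbouring table makes it unlikely that full-dose continuation was intended. For Grade 2 bleeding, 5.4.8 begins "Hold pazopanib until bleeding", asks for recovery to Grade 1 or lower, and then restarts at a reduced dose. Grade 2 bleeding is not a DLT on grade alone. The protocol is therefore stricter with the event it does not call dose-limiting than with the one it does.

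One piece of arithmetic bears on the remedy, not on the defect. Section 2.5 counts a suspension patient as evaluable after at least 24 days at 225 mg/m² in a 28-day cycle (24/28 = 85.7%), or if withdrawn from dosing because of a DLT. With no earlier missed dose, a hold starting on day d leaves d − 1 days at 225 mg/m², and a restart at 160 mg/m² adds none. The condition d − 1 ≥ 24 needs d ≥ 25, so a hold starting on day 24 or earlier leaves at most 23 days. That patient is evaluable only if a hold counts as withdrawal, which 2.5 does not say.

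**The case against.** The best reply is that 5.4.9 was written for venous thrombosis. It speaks of lines and anticoagulation, and its rows fit the graded venous criterion: Grade 2 is not a venous DLT and continues, while Grades 3 and 4 are and do not. Section 5.1.1(b) describes arterial events as ischemia. On that reading there is a missing rule and not an instruction to carry on. The reading is open, since the table never says venous, but it leaves the gap in place.

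A second reply is that the protocol presupposes that patients with a DLT stop dosing: 5.2.2 speaks of holding, 4.2 of resuming, and 2.5 of withdrawal from dosing. That makes unthinking continuation less likely, but none of these is an order, and the one Grade 2 instruction in 5.4.9 points the other way.

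Third, a reader might infer that nothing in the protocol would ever hold drug for a Grade 2 arterial event. The documents do not support that. Section 5.4.2 orders a hold for severe abdominal pain or a worrying examination, and allows the previous dose again only if imaging rules out abdominal pathology. Some visceral ischemia would be caught, which is why the point is limited to peripheral and cerebrovascular events. Physician removal under 8.1(f) is also always available.

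**Conclusion.** The point stands as a dosing-safety inconsistency that should be corrected. One of the three criteria in 5.1.1(b) is at odds with one of the three rows in 5.4.9, or, on the venous-only reading, has no dose rule of its own. The conclusion rests on reading 5.2.2, 4.1.1 and 4.2 as permissions or presuppositions, which is what their wording supports. The size in patients cannot be given: the documents offer no pediatric frequency, describe cerebral ischemia as rare in adults, and do not reproduce the CTCAE grade definitions.

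Two larger conclusions are not supported.

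- A reader might infer that the six-patient suspension review is compromised. Under the current text this needs a chain: a Grade 2 arterial DLT in cycle 1, in one of the first suspension patients, continued under 5.4.9, then stopped before 24 days for another reason. The 23-day figure in the working describes a consequence of adding a hold, and does not measure the present defect.
- A reader might extend the conflict to the third criterion of 5.1.1(b), thrombosis not related to a central line that needs systemic anticoagulation. That depends on whether such an event can be Grade 2, which the documents do not settle.

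The endpoint, sample size and error rates are unaffected. SAP 4.3 records that the study was later declared futile, so the point concerns patients treated under this protocol version.

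**What to change.** - In 5.4.9, limit the Grade 2 continue row to non-arterial events.
- Add a row for attributable Grade 2 arterial events, modelled on 5.3.1(c): hold pazopanib, restart at a reduced dose only if the patient has recovered within 14 days, and otherwise contact the Study Chair before any re-challenge.
- Cross-refer 5.1.1(b) to the new row.
- As a consequential edit only, state in 2.5 that a suspension patient held for a cycle 1 DLT counts as evaluable, so that the new hold does not drop the patient from the six-patient review.

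The cost is a small protocol amendment. A site letter alone is not enough: the letter route in 4.3 covers changes to the concomitant-medication list, while the amendment history at the front of the protocol requires IRB/IEC approval before its protocol changes are implemented. No extra patients, visits or procedures are needed.

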5.2 Dose Modifications for Hematologic Toxicity

All dose modifications should be based on the worst preceding toxicity.

Pazopanib tablets: For step-wise dose reductions, see Appendix II for the dosing nomogram.

Pazopanib powder in suspension: For step-wise dose reductions see Tables 1 and 1a (Section 4.1.1).

5.2.1 For all patients:

If Grade 4 neutropenia occurs,

- a) Pazopanib should be held.
- b) CBCs should be checked at least twice a week (every 3 to 4 days) until ANC $\geq 750/\mu L$.
- c) Subsequent doses of pazopanib should be given at a reduced dose, when $ANC \ge 750/\mu L$.

If Grade 4 thrombocytopenia occurs,

- a) Pazopanib should be held.
- b) CBCs should be checked at least twice a week (every 3 to 4 days) until platelet count \geq 75,000/µL without need for platelet transfusion in the preceding 7 days.

Subsequent doses of pazopanib should be given at a reduced dose, when platelet count \geq 75,000/µL without need for platelet transfusion in the preceding 7 days.

- 5.2.1.1 If dose-limiting myelosuppression occurs as noted in Section 5.1.1,
 - a) The dose of pazopanib should be resumed at a reduced dose, once ANC $\geq 750/\mu L$ and platelet count $\geq 75,000/\mu L$ without need for platelet transfusion in the preceding 7 days.
- 5.2.2 For patients who have a dose limiting hematological toxicity that does not resolve to the parameters defined in Section 5.2.1 within 14 days of holding pazopanib: if re-challenge is to be considered the Study Chair must be contacted and provide approval prior to re-challenge.

5.3 Dose Modifications for Non-Hematological Toxicity

Specific instructions for the management of potential pazopanib side effects are included in Section 5.4.

- 5.3.1 For any non-hematologic dose limiting toxicity as detailed in Section 5.1.2:
 - a) Pazopanib should be held
 - b) If the non-hematologic DLT is a pazopanib specific toxicity, the dosing guidelines in Section 5.4 should be followed
 - c) If the non-hematologic DLT returns to baseline within 14 days of holding pazopanib, subsequent doses of pazopanib should be given at a reduced dose.
 - If toxicity does not resolve to meet continued treatment parameters within 14 days of drug discontinuation, and if re-challenge is to be considered, the Study Chair must be contacted as outlined in Section 4.2 to discuss.
 - If DLT recurs in a patient who has resumed treatment after the maximum allowed dose reductions, the patient must be removed from protocol therapy, unless the patient has been approved for a further dose reduction following discussion with the Study Chair.

5.4 Potential Pazopanib Specific Side Effects

- 5.4.1 Hypertension
 - **Baseline blood pressure** (BP) is defined as the blood pressure obtained at the examination used for study enrollment. This baseline BP should be obtained as follows:
 - 1) Obtain 3 serial blood pressures from the same extremity with the patient in the same position that are separated by at least 5 minutes. Avoid using the lower extremity if possible.
 - 2) Average the systolic blood pressure from the 2^{nd} and 3^{rd} measurements.
 - 3) Average the diastolic blood pressure from the 2^{nd} and 3^{rd} measurements.
 - 4) The baseline BP is the average of the systolic over the average of the diastolic measurements.
 - Elevation in either the systolic or diastolic blood pressure should be considered when following the algorithm below.
 - The upper limit of normal (ULN) is defined as a BP equal to the 95th percentile for age, height, and gender. If ≥ 18 yrs of age, ULN will be defined as a BP of 140/90. See Appendix V.
 - The NCI CTCAE version 4.0 will be utilized to determine the grade of hypertension for reporting purposes.
 - Elevated BP measurements should be repeated on the same day to confirm the elevation. Patients with an elevated BP should have BP measurements performed at least twice weekly until BP is ≤ ULN.
 - The algorithm below will be used to manage pazopanib related hypertension.
 - Hypertension should be managed with appropriate anti-hypertensive agent(s) as clinically indicated. It is strongly recommended that nephrology or cardiology be consulted in the evaluation and management of hypertension.
 - For patients who were on one anti-hypertensive medication at study enrollment and hypertension worsens while on study, further anti-hypertensive therapy may include dose adjustment of the current medication or the addition of a second anti-hypertensive medication.

Elevations in BP are based on systolic or diastolic pressures.

* Elevated blood pressure (BP) measurements should be repeated on the same day to confirm the elevation. Patients with elevated BP at any time should have BP measurements performed at least twice weekly until BP is within the ULN.

[§] ULN (Upper Limit of Normal) is a BP equal to the 95th percentile from age, height, and gender-appropriate normal values (Appendix VIII)

If BP >25 mm Hg above ULN for age (verified) or Grade 4 HTN at any time, hold drug. Study drug should also be held for BP ≤ 25 mm Hg above the ULN age for > 14 days or 35 mmHg above baseline for > 14 days. Antihypertensive agents can be used to control hypertension as clinically indicated after study drug is held.

- Anti-hypertensive therapy should be prescribed as clinically indicated, including the use of multiple anti-hypertensive agents.
- # Baseline BP is defined in Section 5.4.

Arm 1 of algorithm:

• If blood pressure (BP) \leq 95% ile for age, height, and gender: continue pazopanib at the same dose.

Arm 2 of algorithm:

- If $BP \le 10 \text{ mm Hg}$ above the ULN: continue pazopanib at the same dose and recheck the BP within 72 hours.
 - If the BP is \leq ULN on recheck, continue pazopanib at the same dose.
 - $_{\odot}$ If the BP remains above the ULN on recheck, then start/adjust antihypertensive therapy (Section 4.1.5.1) and follow Arm 3 of the algorithm from the point that anti-hypertensive therapy is started/adjusted.

Arm 3 of algorithm:

- If BP is 11 to 25 mm Hg above the ULN on ≥ 2 of 3 measurements or > 35 mmHg above baseline on ≥ 2 of 3 measurements, start/adjust antihypertensive therapy (see Section 4.1.5.1) and continue pazopanib at the same dose. Monitor BP at least twice weekly.
 - If the BP returns to \leq ULN within 14 days, continue pazopanib at the same dose and continue anti-hypertensive therapy.
 - If the BP remains elevated ≥ 25 mm Hg above the ULN or > 35 mm Hg above baseline for more than 14 days after the institution/adjustment of anti-hypertensive therapy, **hold** pazopanib, monitor BP at least every 3 days, and follow Arm 4 of the algorithm from the point that pazopanib is held. The anti-hypertensive therapy should be continued until the BP is less than the ULN.
- If the BP returns to \leq ULN within 14 days, restart pazopanib at a reduced

dose.

- If the BP remains > ULN for more than 14 days, patient must be removed from protocol therapy.
 - If the BP increases to > 25 mm Hg above the ULN despite antihypertensive therapy, **hold** pazopanib, but continue the anti-hypertensive agent(s). Monitor the BP as clinically indicated and follow Arm 4 of the algorithm from the point that pazopanib is held.
- If the BP is ≤ ULN within 14 days, pazopanib may be restarted at a reduced dose.
- If the BP is > ULN for > 14 days, the patient must be removed from protocol therapy (Section 8.1).

Arm 4 of algorithm:

- If BP is > 25 mm Hg above the ULN hold pazopanib, monitor BP, and administer/adjust anti-hypertensive therapy as clinically indicated.
 - \circ If the BP returns to \leq ULN within 14 days, pazopanib may be restarted at a reduced dose.
 - If the BP is > ULN for >14 days, the patient must be removed from protocol therapy (Section 8.1).

Arm 5 of algorithm:

If the participant develops Grade 4 hypertension, **discontinue** pazopanib, monitor BP and administer anti-hypertensive therapy as clinically indicated. A nephrology and/or cardiology consult is recommended. The patient must be removed from Protocol Therapy (Section 8.1).

5.4.2 Abdominal pain:

Abdominal pain is a common symptom with vascular endothelial growth factor (VEGF) receptor antagonists such as pazopanib. Bowel perforations have been reported in clinical trials of pazopanib and with other agents in this class. Bowel perforations have been associated in some patients with tumor in the bowel wall, or diverticulitis, while in others there has been no clear explanation.

Although bowel perforation is a rare event, investigators and study staff at the site are advised to be vigilant of this potential complication in patients receiving pazopanib. Abdominal complaints should be assessed during AE review at every visit. In addition, every physical exam should include a complete abdominal exam. For patients with abdominal complaints and/or abnormal findings on clinical exam, follow the dose modifications and evaluations described below.

Adverse events & descriptions	Dose Modifications & Evaluations
Mild to Moderate abdominal pain or other abdominal complaints with no associated abnormal findings on physical exam	 Continue pazopanib at current dose Implement supportive care as indicated and per institutional standards; consider imaging studies Advise the patient to seek medical attention should their complaints worsen Appropriate follow-up until complaints resolve or origin of the pain is identified. Imaging studies to confirm the absence of abdominal pathology should be performed based on the investigator judgment.
Severe abdominal pain or a concerning abdominal exam	 Hold pazopanib Recommend obtaining appropriate imaging studies to evaluate the patient's specific complaints or exam findings Resume pazopanib at previous dose if imaging studies confirm the absence of abdominal pathology
Confirmed diagnosis of abdominal perforation	1. Remove from protocol therapy

Contact the Study Chair if you need further guidance or would like to discuss an event involving abdominal pain or bowel perforations.

5.4.3 Hepatotoxicity:

Adverse events & descriptions	Dose Modifications & Evaluations
Grade 1 ALT/AST elevation	1. Continue pazopanib at current dose
	2. Check liver function tests $(LFTs)^1$ as per
	Evaluations table in Section 7.1
Grade 2 ALT/AST elevation without	1. Continue pazopanib at current dose
bilirubin elevation (defined as total	2. Consider performing the following to exclude
bilirubin ² \leq 1.5 x ULN or direct bilirubin	hypersensitivity and other contributing factors:
\leq 35% of total bilirubin) and without	Eosinophil count
hypersensitivity symptoms (eg: fever,	• Viral serology ⁴ for hepatitis A, B and C
rash)	• Liver imaging (ultrasound)
	3. Monitor patient closely for clinical signs and
	symptoms
	4. Perform LFTs ¹ weekly (or more frequently if
	clinically indicated) until AST/ALT \leq Grade 1

	1	· · · · · · · · · · · · · · · · · · ·
≥Grade 3 ALT elevation without bilirubin elevation (defined as total bilirubin ² ≤ 1.5 x ULN or direct bilirubin ≤35% of total bilirubin) and without hypersensitivity symptoms (e.g., fever, rash)	L 1. 2. 3. 4. 5.	 iver Event Interruption/Stopping Criteria³: Hold pazopanib. Repeat LFTs¹ within 72 hrs to confirm ≥Grade 3 ALT elevation; if confirmed: Perform the following assessments to exclude hypersensitivity and other contributing factors: Eosinophil count Optional viral serology⁴ for hepatitis A, B, C and E, cytomegalovirus⁴, Epstein Barr virus⁴ (IgM antibody, heterophile antibody, or monospot testing) Liver imaging (Ultrasound) Monitor patient closely for clinical signs and symptoms Perform LFTs¹ weekly (or more frequently if clinically indicated) until ALT reduced to ≤ Grade 1 Pazopanib may be held for up to 14 days, if ALT returns to ≤ Grade 1 and patient is benefitting from treatment, pazopanib may be resumed at a reduced dose following Novartis / Study Chair approval (contact the Sponsor Medical Lead and the Study Chair via email or phone to start the approval process). If approval for retreatment is granted, the patient must be reconsented (with a separate informed consent) specific to hepatotoxicity. For patients on tablets dose reductions are as follows: If on 800 mg, then reduce to 400 mg daily If on 600 mg, then reduce to 400 mg
		 daily If on 600 mg, then reduce to 400 mg daily If on 400 mg, reduce to 200 mg daily For patients on powder suspension: Follow the sequential dose reduction (Section 4.1.1.), one dose level reduction
	6.	is required (e.g. from 225 mg/m2 to 160 mg/m2) Following re-introduction of pazopanib, continue
		to monitor ALT weekly for 2 cycles, if $ALT \ge$ Grade 2 recurs permanently discontinue pazopanib

-
Liver Event Stopping Criteria ³ :
1. Discontinue pazopanib permanently
2. Recheck LFT's', serum creatinine
phosphokinase (CPK) and collect PK sample. Also check:
 Eosinophil count Optional viral serology⁴ for hepatitis A, B, C and E, cytomegalovirus⁴, Epstein- Barr virus⁴ (IgM antibody, heterophile antibody, or monospot testing) Anti-nuclear antibody⁴, anti-smooth muscle antibody⁴, anti-mitochondrial antibody⁴ Liver imaging (Ultrasound) Recommend referral to (consult) a pediatric gastroenterologist/hepatologist. Monitor patient closely for clinical signs and symptoms. Perform full panel LFTs¹ weekly or more frequently if clinically indicated until LFTs are reduced to Grade 1
 Isolated hyperbilirubinemia (in the absence of elevated ALT or other signs/symptoms of liver injury) does not require dose modification. Study treatment inhibits UGT1A1 and OATP1B1, which can cause elevation of indirect (unconjugated) bilirubin in the absence of liver injury If total bilirubin is >1.5 ULN in the absence of ALT elevation, fractionation of bilirubin should be performed. If the bilirubin is predominantly indirect (≥65%) indirect (unconjugated), continue study treatment at the same dose. If bilirubin is >35% direct (conjugated), study treatment may also be continued however, further evaluation should be undertaken for underlying cause of

¹LFTs include: AST, ALT, alkaline phosphatase, GGT and total bilirubin.

²Serum bilirubin fractionation should be performed if testing is available. If testing is unavailable and a patient meets the criterion of total bilirubin > 1.5 x ULN, then the event should be promptly reported as defined. ³When a liver chemistry event meets the Liver Event Interruption Criteria, or Liver Event Stopping Criteria, blood samples should be obtained for clinical laboratory testing by the central laboratory (Liver Event Kits will be provided for this purpose).

⁴These extra tests will be performed centrally

5.4.4 Electrolyte Abnormalities:

Serum K⁺, Ca^{++} , Mg^{++} , phosphate levels should be monitored given the risk of prolonged QTc. If serum Ca^{++} is abnormal, ionized calcium should be obtained and interventions based on ionized calcium only.

Pazopanib should be held and an EKG obtained for

- Hypokalemia or hyperkalemia \geq Grade 2
- Hypocalcemia or hypercalcemia \geq Grade 3
- Hypophosphatemia or hyperphosphatemia \geq Grade 3
- Hypomagnesemia or hypermagnesemia \geq Grade 3

These laboratory values should be corrected as soon as possible in a manner consistent with good medical judgment. Pazopanib may be resumed at a reduced dose when:

- Hypokalemia or hyperkalemia is Grade 1 or within institutional limits
- Hypocalcemia or hypercalcemia is \leq Grade 2
- Hypophosphatemia or hyperphosphatemia is \leq Grade 2
- Hypomagnesemia or hypermagnesemia is \leq Grade 2.

Even though pazopanib administration is allowed at these lower laboratory toxicity grades, every effort should be made to correct the abnormal lab values to normal if possible.

5.4.5 Proteinuria:

- If urinalysis shows ≥ trace protein then obtain a urine protein: creatinine ratio (UPC).
- If the UPC is \geq 1, then obtain a 24-hour urine collection for protein estimation.
- If the urine protein is ≥ 3.5 g/24-hours then hold pazopanib and reassess urine protein weekly.
- If the urine protein decreases to < 3.5 g/24 hours in < 21 days then resume pazopanib at a reduced dose.
- Monitor the 24 hour urine protein or UPC weekly for 2 consecutive weeks once pazopanib is resumed.
- If pazopanib is held for ≥ 28 days then the patient must be removed from protocol therapy.
- 5.4.6 Cardiac Function:

5.4.6.1 Left Ventricular Systolic Dysfunction:

Adverse events & descriptions	Dose Modifications & Evaluations
LV EF <lln <math="" but="">\geq 50% OR</lln>	Continue drug and repeat Echo on Day 28 of
LV SF \leq LLN but \geq 24% without symptoms	subsequent cycle
of cardiac dysfunction	
LV EF 40 – 49% OR	Hold pazopanib and obtain repeat Echo in 7
LV SF 15 – 23% OR	days. If toxicity confirmed, then remove
Absolute decrease in SF \geq 8 percentage	from protocol therapy.
points from baseline	If not confirmed, then resume drug at reduced
	dose and repeat Echo 14 and 28 days after
	resuming pazopanib. If any 2 Echos
	demonstrate LV EF 40 - 49% OR LV SF 15 -
	23%
	$OR \ge 8$ percentage point decrease in SF then
	remove from protocol therapy and refer to
	pediatric cardiologist
Grade 3 LV EF decreased OR	Remove from protocol therapy – refer to
Grade 3 LV SF decreased	pediatric cardiologist

• Cardiac evaluation by Echo but MUGA (Multiple-Gated Acquisition) may be used if clinically indicated

5.4.6.2 QT Prolongation:

Guidelines for the management of prolonged QT interval are as follows: Measure the QT interval (from the start of the Q wave to the end of the T wave) and the preceding RR interval. The corrected QT interval using the Bazett's formula (QTcB interval) will be calculated as the QT interval (msec) divided by the square root of the RR interval (msec). Only the Bazett's formula should be used to calculate the corrected QT interval.

- QTcB interval < 500 msec: No specific therapy needed. Continue pazopanib at the same dose. Serum K⁺, Ca⁺⁺, Mg⁺⁺, and Phos should be monitored and repleted if low (see Section 5.4.4).
- QTcB interval ≥ 500 msec: Hold pazopanib, review concomitant medications, and replete serum K⁺, Ca⁺⁺, Mg⁺⁺, and Phos as needed. The EKG should be repeated within 7 days and if the QTcB interval is < 500 msec then resume pazopanib at a reduced dose. If the QTcB interval remains ≥ 500 msec, the patient must be removed from protocol therapy.
- 5.4.7 Delays in Wound Healing:

Patients treated with VEGF blocking agents appear to have an increased risk of wound healing complications. Therefore, if patients require elective major surgery on study, pazopanib should be held for 14 days prior to surgery and for 14 days after surgery (see Section 3.3.7). Pazopanib should not be restarted if there is evidence of wound healing complications such as a wound infection. Patients who require surgery less than 14 days from treatment with pazopanib should be monitored closely for wound complications. Patients who require major surgery during Cycle 1 of therapy must be removed from protocol therapy.

